14.3.2. Subject Data Confidentiality

All information and data collected for this study protocol concerning subjects or their participation in this investigation will be considered confidential. Only authorized Sponsor personnel or a Sponsor representative will have access to these confidential files. All data will be handled in accordance with applicable local laws. Authorized FDA personnel or Regulatory Authorities have the right to inspect and copy all records pertinent to this investigation. All data used in the analysis and reporting of this investigation will be without identifiable reference to specific subject name.

15. QUALITY

Quality Control is defined as the operational techniques and activities, such as monitoring, undertaken within the quality assurance system to verify that the requirements for quality of the study related activities have been fulfilled.

Quality Control should be applied to each stage of data handling to ensure that all data are reliable and have been processed correctly.

15.1. Site Selection

The sites should have previously participated in clinical studies and must have adequate experience, time, staff, and facilities to perform all required duties. Sites must permit clinical trial related monitoring, audits, IRB review, and regulatory inspections, providing direct access to source data/documents, as appropriate

15.2. PSG Data

This study will utilize a sleep core lab to ensure consistency in scoring across all participants and all sites. The sleep core lab member responsible for scoring the participant PSGs will be blinded to the subject's randomization group as well as to the therapy settings of the participant. It is the responsibility of the site investigator to collect and send this data to the sleep core lab.

15.3. Training

The clinical monitor will conduct an initiation visit at each site to review relevant documentation such as the clinical protocol, study manual, Astral Instructions for Use, GCP, applicable regulations, and investigator's obligations with site study personnel. In addition, training on the Data Management System will be conducted. If new study staff members are employed at the site after the initiation meeting, experienced site personnel must train new employees as noted above and document the training (contact the clinical monitor for instructions on how to document the training).

15.4. Site Monitoring

The study will be initiated by the study monitor, or designee, during an on-site visit after all required documents have been processed. Qualified clinical monitors will perform on-site monitoring visits as frequently as is deemed necessary.

During the site visits, the monitor will compare the data entered into the eCRF with the source documents. In addition, the monitor will verify that standards of Good Clinical Practice (GCP) are being followed. Findings from the review of eCRFs, source documents and study conduct will be discussed with the investigator. The Sponsor expects that, during monitoring visits, the study coordinator and investigator will be available, the source documentation will be available and a suitable environment will be provided for review of study related documents

16. RESPONSIBILITIES

16.1. Clinical Investigator Responsibilities

With the approval of their institution's IRB/EC, qualified investigators will conduct the CAT-HF clinical investigation in accordance with the Declaration of Helsinki: "Recommendations Guiding Medical Doctors in Biomedical Research Involving Human Subjects". Each site principal investigator and their co-investigators are responsible for the following:

- Completion of all required agreements
- Screening and evaluation of subjects
- Strict adherence to the Clinical Protocol, Study Manual of Procedures and all Federal Regulations
- Supervising investigational device use and return
- Obtaining informed consent prior to study related procedures and the collection of data during study and follow-up examinations in a timely manner
- Timely reporting of all SAEs and UADEs
- Providing death notes, when applicable

It is acceptable for the site principal investigator to delegate one or more of the above functions to an associate or co-investigator, however, the site principal investigator remains responsible for proper conduct of the clinical investigation and signing an investigator agreement. The investigation is non-transferable to other centers attended by the investigator unless prior approval is obtained from the appropriate IRB/EC and the Sponsor.

16.2. Sponsor Responsibilities

The Sponsor will provide each site with a study Manual of Procedures and study materials. The Sponsor will train study personnel on the clinical study protocol and procedures. Clinical monitors will conduct site visits in order to ensure the site procedures are being carried out in accordance with the clinical study protocol and GCP. Clinical monitors will ensure that the study is progressing as expected, study data are accurate and up to date, data recording is complete, and protocol deviations are recorded and reviewed with the PI. Throughout the study period, the clinical monitor will be available to address any issues that may arise. This availability includes access by phone, fax, and/or e-mail. An additional site visit or conference call may be scheduled at the end of the study period to formally close the clinical study.

18. APPENDIX A – ASTRAL CLINICAL GUIDE

19. APPENDIX B – INFORMED CONSENT FORM

20. APPENDIX C - CRFs

Statistical Analysis Plan (SAP)

Protocol Title: Astral VAPS AutoEPAP Clinical Trial
Study #: MA-15-12-15
Protocol Version/Date: Revision 4.0, 06Jun2016
Sponsor: ResMed Corporation
Author: [name], Willes Consulting Group, Inc.
SAP Version/Date: Version 1.0, 23Sep2016

Approved By:

Name, Title	Signature	Date
[name], VP Medical Affairs		
[name], Sr CRA, Medical Affairs		
[name], President, Willes Consulting Group		

Table of Contents

Statistical Analysis Plan (SAP)	1
1. Study Synopsis.....	3
2. Analysis Populations.....	3
3. Poolability analysis	3
4. General Statistical Analysis Guidelines	4
5. Subject Accountability.....	4
6. Primary Objective and Endpoint.....	4
6.1. Statistical Analysis of the Primary Endpoint	4
6.2. Subgroup Analyses of the Primary Endpoint.....	5
7. Statistical Analysis of Secondary Objectives.....	5
8. Additional Analyses	5
9. Handling of Missing Values	5
10. Justification of Sample Size.....	6
11. Protocol Deviations.....	6
11. Statistical Software and Programming.....	6
12. References.....	6

1. Study Synopsis

Version 3.0 of the protocol excluded subjects who are dependent on ventilator support. During the active stage of this trial, the iVAPS (with manual EPAP) algorithm on the study device (Astral) was cleared by the FDA. The IFU can be applied to both ventilator dependent and non-dependent patients. An increase in enrollment to 40 subjects will ensure that there is a mixture of both non-dependent ventilator support patients (v3.0 of protocol) and ventilator dependent (v4.0 of protocol) patients enrolled. [Note: The assumption is that primary endpoint of upper airway stability will not differ between ventilator dependent and non-dependent groups. A subgroup analysis of the primary endpoint comparing dependent and non-dependent patients will be generated. The expectation is that approximately 10% of the total enrollment goal of 40 will be ventilator dependent].

2. Analysis Populations

The populations are defined as follows.

- The Enrollment population is defined as all patients who are randomized for the study and begin the first study PSG night.
- The Intent-To-Treat (ITT) is defined as all patients in the Enrollment population who meet the inclusion/exclusion criteria.
- The Completed Cases (CC) population is defined as all patients in the ITT population who complete all study visits.

The primary endpoint analysis will be based on the CC subject population. A sensitivity analysis of the primary endpoint will be generated for the Enrollment population for patients who complete all study visits. An additional sensitivity analysis for the primary endpoint will be generated for the ITT population. The ITT population may contain some subjects who complete that first study PSG visit but not the second study PSG visit. This will require the use of imputation methods for missing values which are documented in Section 9.

All safety analyses will be generated for subjects in the Enrollment population. All secondary endpoints will be generated using the CC population.

3. Poolability analysis

The issue of poolability of the data entails two features: the combining of data across study sites and the method of computation of an overall estimate for study endpoints. The justification for combining of data across sites is based on the clinical assessment provided by Meinert (1): the clinical study will be conducted under a common protocol for each investigational site, the study sites will be monitored for protocol compliance, and the same data gathering instrument and method will be used in every site.

The justification for pooling all the data to estimate a common effect across study sites requires the homogeneity of response across study sites. An analysis of variance (ANOVA) of the differences will be generated to test whether the investigational sites differ with respect to primary study endpoint for the CC population (only the site will be included in this analysis model). The test of in homogeneity of response will be based on a two-sided significance test at the 0.15 level of significance. If the sites differ by this test, then a second analysis will be done including study site and all baseline characteristics that have $P < 0.10$ in

the analysis of baseline characteristics by site to understand if the imbalance in the primary endpoint between sites is related to an imbalance in baseline characteristics.

The analysis of study sites may require the formation of pseudo-sites because the small study sites will not provide appropriate information to allow the analysis above. Study sites with fewer than 6 subjects will be combined into pseudo-sites for the poolability analysis using the following method. The smallest study site with less than 6 subjects will be combined with the next smallest study site. These two sites may be combined with a third site if the combined number of patients remains less than 6. The combination of sites will be halted if combining these sites makes the new pseudo-site the largest study site. Assigned pseudo-sites will be used for the analysis of poolability described above.

4. General Statistical Analysis Guidelines

The number of observations, mean, median, standard deviation, standard error, minimum and maximum will be calculated for continuous variables, unless otherwise stated. The number of significant digits reported will be as follows: minimum and maximum will have the same number of significant digits as the raw data; the mean, median, standard deviation, and standard error will be reported with one more significant digit than the raw data. Frequencies and percentages will be calculated for categorical data using one significant digit for percentages.

As a routine function in applying statistical procedures, the assumptions underlying those procedures will be evaluated. Equal variance will be tested by Folded F-test or Levene's test depending on the number of groups being compared. Tests for normality will not be done for continuous variables, but data will be inspected for symmetry through histogram plots and severe outliers will be investigated.

5. Subject Accountability

Subjects who withdraw from the study will be tabulated with the reasons for the withdrawal. Compliance with study visits will also be presented.

6. Primary Objective and Endpoint

The primary outcome is the Oxygen Desaturation Index (ODI4%). The primary aim of this protocol is to compare ODI values following the use of the AutoEPAP algorithm with the use of manual EPAP on the Astral ventilator.

The null and alternative hypothesis is based on a non-inferiority test using a non-inferiority margin (d) of 2 events/hour.

H0: $\mu_{A-B} > d$ (new algorithm is inferior)

H1: $\mu_{A-B} \leq d$ (new algorithm is non-inferior)

Where μ_{A-B} is the mean paired difference in ODI4% comparing AutoEPAP and manual EPAP algorithms, and d equals the non-inferiority margin.

6.1. Statistical Analysis of the Primary Endpoint

The primary hypothesis will be tested using a one-sided paired t-test of the difference in ODI between Auto and Manual EPAP and compared to a non-inferiority margin for ODI4% of 2 events/hour. Additionally, the 95% upper one-sided confidence bound for the mean paired difference in ODI between manual and Auto EPAP will be calculated.

A cross-over analysis will be generated to investigate the influence of a possible period effect on the primary endpoint, paired change in ODI4% between Auto and Manual EPAP. Based on previous studies, ResMed does not expect the randomization order in which the subject used Auto versus Manual EPAP to affect the differences in ODI between the methods. A two-sample t-test comparing the two randomized treatment groups based on an alpha of 0.05 will be utilized for this analysis.

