9. STUDY SCHEDULE

A summary of the procedure is summarized in Figure 2.

Figure 2. Summary of trial procedure

Visit 1

- Provide consent
- Meet eligibility criteria
- Collect baseline data

9.1. Visit 1

Participants will be recruited from existing hospital patient databases. Participants will be pre-screened and those meeting the required criteria will be contacted by the investigators via follow up phone call or during an office visit, and asked if they wish to take part in the study.

Participants wishing to participate will attend the sleep clinic/hospital where written informed consent will be obtained (Appendix B). All participants will be checked for study eligibility using the Inclusion/Exclusion criteria of this protocol. Participants who do not meet the eligibility criteria will not be included in the study. Participants meeting the eligibility criteria will have baseline information collected, including participant demographics, medical history, and information about the participants' current therapy. If available, the following information will also be collected into the subject chart: diagnostic sleep study report, their most recent spirometry report, and at the physicians' discretion, a capillary blood gas test.

9.2. Visit 2

Participants will attend an office visit where they will be randomized (1:1) to receive iVAPS with AutoEPAP or iVAPS with manual EPAP first. Participants will be randomized according to a computer-generated randomized list.

Participants will undergo an overnight PSG at the site per their randomized group assignment. Full PSG set-up, data acquisition, monitoring and reporting will be performed using the AASM 2007 criteria. Therapy will be delivered using the clinical trial device, Astral. At least 4 hours of recording will be required.

Participants' trial devices will be setup according to the therapy settings detailed in the Therapy section of this protocol. The set-up of manual EPAP or AutoEPAP settings shall occur before lights out. Study staff will also set up the subject to test PtCO₂. This may be done with a device clipped to the outside of the subject's ear, and does not introduce risk to the subject.

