Serious adverse events and events related to the Astral device will be tabulated for the Enrollment population, presenting the number of patients having one or more of each event and the associated percentage. A distinction will be made as to whether the subjects having adverse events were part of the ITT or Enrollment populations. In addition, a listing of these events will be presented, including the event description, time of occurrence, severity, outcome, action taken and relationship to the study device.

A separate listing of all other adverse events (non-serious and not related) occurring during the study period will be generated, including the event description, time of occurrence, severity, outcome, action taken and relationship to the study device.

9. Handling of Missing Values

The primary analysis will be based on the CC population. A multiple imputation sensitivity analysis will be done in the following way. Patients who dropout between the first and second PSG visit periods, will

have their second PSG visit data imputed, using the multiple imputation procedure MI in SAS. The imputation model will include randomization group and first period ODI4% as predictor variables. Results will be pooled using the MIANALYZE procedure in SAS.

10. Justification of Sample Size

Using a sample size calculation based on a normal distribution, the sample size required for 80% power to detect a difference in ODI of 1 event/hour, using a one-sided significance level of 0.05, was calculated to be 23 subjects assuming a SD of 1.55 in the Astral VAPS AutoEPAP Clinical Trial Protocol.

[Using the normal approximation formula for sample size as written in the protocol, I calculate a sample size of 15 patients required based on SD=1.55, beta=0.2, one-sided alpha=0.05, and a detection difference between groups of 1. Using a two-sided alpha of 0.05, the sample size is 19. Using PASS software (2) which uses the t distribution to calculate the sample size for paired means rather than the z distribution, the sample size is 17 for a one-sided alpha of 0.05, and 21 for a two-sided alpha of 0.05].

11. Protocol Deviations

Protocol deviations occurring during the study will be tabulated.

11. Statistical Software and Programming

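### SAP 6.1: the primary paired t-test has no period term in a randomized-order crossover; a period-adjusted estimate is a cheap gain in precision and in validity given the observed split

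*SAP*

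**What the plan says.** Protocol 9.2 randomizes the order of the two modes: "they will be randomized (1:1) to receive iVAPS with AutoEPAP or iVAPS with manual EPAP first". Protocol 10 prefers consecutive nights and allows up to a week between them.

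SAP 6.1 sets the primary test: "The primary hypothesis will be tested using a one-sided paired t-test of the difference in ODI between Auto and Manual EPAP", which is "compared to a non-inferiority margin for ODI4% of 2 events/hour". It adds that "the 95% upper one-sided confidence bound for the mean paired difference in ODI between manual and Auto EPAP will be calculated". Neither the test nor the bound has a term for period or sequence. Protocol 12 has none either.

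SAP 6.1 deals with period separately: "A cross-over analysis will be generated to investigate the influence of a possible period effect on the primary endpoint". The method is given as: "A two-sample t-test comparing the two randomized treatment groups based on an alpha of 0.05 will be utilized for this analysis". Comparing the paired differences between the two order groups is the right test for a period effect, but neither document says what follows from a significant result. The reason offered for not adjusting rests on earlier studies and reads: "ResMed does not expect the randomization order in which the subject used Auto versus Manual EPAP to affect the differences in ODI between the methods". No figure accompanies that statement.

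Randomization group does enter the multiple-imputation model in SAP 9, but only for a sensitivity analysis.

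**The concern.** In a two-period crossover, a shift between night 1 and night 2 enters the Auto-minus-Manual difference with a plus sign in one sequence and a minus sign in the other. A one-sample analysis of the pooled differences cannot separate this shift from random variation. Two things follow. The standard deviation is inflated, so the bound is wider than it needs to be. If the sequences have unequal numbers of completers, the shifts do not cancel and the mean is biased.

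What is at stake is the precision of the non-inferiority bound and its validity given the split that this trial happens to have. There is also a reporting problem. If the period test is significant, the SAP gives no rule for reading the primary result, so any rule would be chosen after the data are seen.

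**Working it through.** **Inputs.**
- SD 1.55 and expected mean difference 0: Protocol 6.2.4. I take 1.55 as the SD of the paired difference within a sequence, which is an assumption.
- Margin 2/h: SAP 6 and 6.1.
- One-sided alpha 0.05: SAP 10, "using a one-sided significance level of 0.05", and Protocol 12.
- Completers: at least 36 of up to 40 randomized, with 10% dropout (Protocol 3). 36/0.9 = 40 agrees.
- Night effect p (night 1 minus night 2): not in the documents. I assume 0.5 and 1/h, with 0 as reference.

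**The plan's own figures.** The plan gives no figure for a period effect. The protocol's sample-size formula with 1.55, a difference of 1 and 80% power gives (1.645 + 0.842)² × 1.55² = 14.85, so 15 one-sided, and (1.960 + 0.842)² × 1.55² = 18.86, so 19 two-sided. Both match the bracketed note in SAP 10. The protocol's 22.84 needs a one-sided alpha of 0.0125. That is a separate matter and nothing below depends on it.

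**Formulas.** Let n1 be the completers with AutoEPAP first, n2 those with manual EPAP first, and n = n1 + n2.
- Mean difference: true difference + p in the first group, true difference - p in the second.
- Bias of the pooled mean: p × (n1 - n2)/n. At p = 1 this is 4/36 = 0.11/h for 20/16 and 8/36 = 0.22/h for 22/14.
- Expected variance of the pooled differences: 1.55² + p² × 4·n1·n2/[n(n - 1)].
- Period-adjusted estimate: the average of the two sequence means, with SE = (s/2) × √(1/n1 + 1/n2), s being the pooled within-sequence SD on n - 2 df.

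**Half-width of the bound at 18/18** (t quantile 1.690 on 35 df):
- p = 0: 1.690 × 1.55/6 = 0.437
- p = 0.5: 1.690 × √(2.4025 + 0.257)/6 = 0.459
- p = 1: 1.690 × √(2.4025 + 1.029)/6 = 0.522

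The simulated averages are 0.433, 0.456 and 0.518. They are slightly lower because a sample SD averages a little below the true SD. The adjusted half-width is 0.434 at every p.

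**Type I error at a true difference of 2/h** (simulation, 400,000 trials per case; where two values are given, they are for the two directions of imbalance):

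| Split | p | Paired t-test | Period-adjusted |
|---|---|---|---|
| 18/18 | 0 | 5.0% | 5.0% |
| 18/18 | 0.5 | 4.2% | 5.0% |
| 18/18 | 1 | 2.5% | 5.0% |
| 20/16 | 1 | 0.9% or 6.2% | 5.0% |
| 22/14 | 0.5 | 1.6% or 9.6% | 5.0% |
| 22/14 | 1 | 0.3% or 13.5% | 5.0% |

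The higher values arise when the imbalance makes AutoEPAP look better than it is, for example when ODI is higher on night 1 and more completers had manual EPAP first.

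**How likely is a bad split?** With an unblocked list, Binomial(36, 0.5) gives 62% for 20/16 or worse and 24% for 22/14 or worse. Both figures count the two directions together, so the adverse direction of 22/14 or worse has 12%. From a balanced 20/20 list, losing the planned four subjects gives 20/16 at worst. The protocol mentions a computer-generated list but does not say whether it is blocked.

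**Averaged over the allocation.** Under simple randomization the paired test's type I error is 5.0% at p = 0.5 and at p = 1. With 20/20 and four random losses it is about 4.2% and 2.8%.

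**Power at n = 36, 18/18.** At a true difference of 0, both methods have about 100% power. At a true difference of 1 and p = 1, the paired test has 96.5% and the adjusted test 98.4%.

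**Power of the SAP's period test at 18/18.** About 47% at p = 0.5 and 96% at p = 1.

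**The case against.** The defence has several good points.

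- **Overall validity.** If order is assigned independently for each subject, the paired differences are independent and identically distributed even with a night effect, so the paired t-test keeps its 5% level. If the list is balanced, the test is conservative. This stands. A reader might infer that the 5% level holds only without a period effect, but that is wrong on average. The inflated figures are conditional on an adverse split.
- **Size of the night effect.** The 1/h value has no source in the documents. Protocol 4.1 reports mean treated AHI of 1.7 and 1.3/h in an earlier trial. That is AHI rather than ODI, but 1/h would be most of such a residual rate. The sponsor also expects no order effect. This stands as a reason to treat 1/h as a large assumed value and to show 0.5/h beside it. It does not show that the effect is zero.
- **Double counting.** The 1.55 comes from an earlier study and may already contain some night-to-night shift, in which case part of the widening is already planned for. This stands.
- **Period is examined.** The SAP does test it, and at 1/h that test has 96% power. A reader might call the test weak or say that the primary analysis is made to depend on it. The first is true only for smaller effects, and the second is not what SAP 6.1 says. What remains is that the result changes nothing in the plan.
- **Protocol 12's rejection rule** for manual-EPAP ODI of 10/h or more could unbalance the sequences. It would tend to remove more subjects whose manual night fell on the worse night, which pushes the bias in the conservative direction. It is not a route to inflation.

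**Conclusion.** The point holds as a cheap improvement. The primary analysis leaves out a design factor that is already recorded. For an assumed night effect of 0.5 to 1/h, this costs 0.02 to 0.08/h of half-width when the sequences are equal. When they are unequal, the error rate given the split departs from 5% in either direction.

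It is not an overall error-rate failure. The 13.5% figure needs three things together: a night effect of about 1/h, a split as uneven as 22/14, and the adverse direction. Reading it alongside the 24% probability would overstate the risk, because half of that probability belongs to the direction in which the error is 0.3%. Such a split also cannot come from a balanced list with the planned dropout.

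At the planned difference of 0, a half-width of 0.52 instead of 0.43 against a margin of 2 changes no conclusion. The adjustment would matter more if the true difference lay near the margin or the SD were well above 1.55.

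**What to change.** In SAP 6.1, before the data are unblinded:

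1. Define the primary estimate as the unweighted average of the two sequence-specific mean Auto-minus-Manual differences. With complete pairs this equals a model with mode, period and subject.
2. Take the one-sided 95% upper bound from the pooled within-sequence SD on n-2 df and compare it with 2/h.
3. State that this analysis is primary whatever the period test shows, and report the period effect with a confidence interval.
4. Keep the unadjusted paired t-test as a supportive analysis.

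The cost is SAP wording and one degree of freedom (at n = 36 the t quantile moves from 1.690 to 1.691), with no new data. If the sequences turn out unbalanced and there is no night effect, the adjusted bound is slightly wider: 0.445 against 0.434 at 22/14.
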